20.4 Full Analysis Set

The full analysis set (FAS) is defined as the subjects who received at least one injection of Rabies vaccine and had at least one blood sample drawn and valid post-injection serology result (i.e. a result different from “NR” or missing).

Subjects will be analyzed by the treatment group to which they were randomized.

20.5 Populations Used in Analyses

The immunogenicity analysis will be performed on the PP. The kinetic analysis will be performed on the FAS.

21 Handling of Missing Data and Outliers

21.1 Immunogenicity

For the computation of GMTs, a titer reported as < LLOQ will be converted to a value of 0.5 LLOQ.

For calculating fold-rise and titer ratio (GMTR), < LLOQ will be converted to 0.5 LLOQ for a numerator and < LLOQ will be converted to LLOQ for a denominator

Any titer reported as > ULOQ (upper limit of quantization) will be converted to ULOQ.

Missing data will not be imputed.

Potential outliers will be identified using histograms and modified box plots or normal probability plots, when appropriate. Choice of subsequent tests for outliers (e.g. Grubbs, Tietjen-Moore and ESD) will depend on the number and nature of suspected outliers and may require data transformation. Bootstrapped estimates of standard errors may also be reported. Sensitivity analysis of effect of outliers on descriptive statistics will be conducted, and if necessary descriptive statistics that include and exclude outliers will be reported.

22 Determination of Sample Size and Power Calculation

The planned sample size is 60 subjects, who will be randomly allocated (2:2:2:2:1:1) to six treatment groups. The sample size was chosen empirically, based on sample sizes of other exploratory studies of this general type. This exploratory study is not powered to formally test equivalency or non-inferiority in immunogenicity among groups according to vaccination dosage and route of administration.

23 Ethical and Legal Issues and Investigator / Sponsor Responsibilities

23.1 Ethical Conduct of the Trial / Good Clinical Practice

This trial will be conducted in accordance with the Seoul revision of the Declaration of Helsinki as far as adopted by the concerned regulatory authorities, as well as in accordance with GCP as defined by International Conference on Harmonization (ICH), and with the applicable national and local requirements regarding ethical committee review, informed consent, and other statutes or regulations regarding the protection of the rights and welfare of human subjects participating in biomedical research.

23.2 Source Data and Source Documents

“Source data” are the data contained in source documents. Source documents are original documents or certified copies, and include, but are not limited to medical and hospital records, screening logs, informed consent / assent forms, Telephone Contact Logs, and worksheets. The purpose of trial source documents is to document the existence of subjects and to substantiate the integrity of the trial data collected. Investigators must maintain source documents so that they are accurate, complete, legible, and up to date.

The subject screening and enrollment log should list all individuals contacted by the Investigators to participate in the trial, regardless of the outcome.

23.3 Confidentiality of Data and Access to Subject Records

Prior to initiation of the trial, the Investigator will sign a fully executed confidentiality agreement.

The IRBs, and regulatory agencies, including the FDA, require direct access to all study records, and will treat these documents in a confidential manner.

23.4 Monitoring, Auditing, and Archiving

23.4.1 Monitoring

Before the start of the trial (i.e., before the inclusion of the first subject), the Investigators and the Monitoring representative will meet at the site-initiation visit to discuss the trial

protocol and the detailed trial procedures. Emphasis will be placed on inclusion and exclusion criteria, visit timing, informed consent procedures, eCRF completion, and the handling of samples and products.

The monitoring staff will ensure and document that all material to be used during the trial has been received at the site; and that the study investigator team and local monitoring staff have been properly informed about the trial, GCP and regulatory requirements.

After the start of the trial, the monitoring staff or a representative will be in regular contact with the investigational team through telephone calls and regular follow-up visits. The Investigator or delegate must be available for these visits, and must allow the monitoring staff direct access to subject medical files and eCRFs. During these visits, the monitoring staff will:

- Evaluate the quality of the trial progress (adherence to protocol and any study-specific guidelines, quality of data collection and document completion, signature of consent forms, occurrence of SAEs, sample and product management, cold-chain monitoring, archiving, and direct observation of study procedures during the trial.)
- Source-verify completed eCRFs and any corresponding answered queries
- Determine the number of complete or ongoing issues identified at monitoring visits (e.g., protocol violations, SAEs). Any identified problems will be discussed with the Investigator, and corrective or preventive actions will be determined, as appropriate.
- review that all protocol procedures have been completed and the data have been entered into the eCRF. All data-related queries must be completed prior to database lock.

At the end of the trial, a close-out visit will be performed to ensure that:

- The center has all the documents necessary for archiving.
- All samples have been shipped to the appropriate laboratories.
- All unused materials and products have been either destroyed or returned.

23.4.2 Audits and Inspections

A quality assurance (QA) audit may be performed at any time to verify that the trial has been conducted according to the protocol, GCP and ICH requirements, and other applicable regulations. An inspection may be conducted by regulatory authorities. The Investigator must allow direct access to trial documents during these inspections and audits.

Title: Immunogenicity of a Two vs Three dose, Intradermal (ID) vs Intramuscular (IM) Administration of a Licensed Rabies Vaccine for Pre-Exposure Vaccination

NCT number: 02374814

Document date: 05 December 2016

**Immunogenicity of a Two vs Three dose, Intradermal (ID) vs Intramuscular (IM)
Administration of a Licensed Rabies Vaccine for Pre-Exposure Vaccination**

Randomized, open-label, single center trial in adults aged 18 to 60 years in the US

Statistical Analysis Plan (SAP)

Version 1.1 Dated 05 Dec 2016

Funder's Representative

[name]
Walter Reed Army Institute of Research
[name]
[name] 20910

Principle Investigator:

[name]
Upstate Medical University
[name]
Syracuse, NY 13210

Licensed Products:

The RabAvert® Rabies Vaccine

Form /Route:

Intradermal and Intramusclar

Indication For This Study:

Comparison of Dose and Schedule

**Medical
Officer:**

[name]
Upstate Medical University

**Funder's Clinical Development
Director:**

[name]
USAMMDA
[name]
Ft. Detrick, MD 21702
[contact]
[contact]

Study Site/PI Location:

Center for Global Health and Translational Science
Upstate Medical University
Syracuse, NY

**Study Statistician and
SAP Author:**

[name]
Associate Professor, Department of Health and Preventive Medicine
SUNY Upstate Medical University
[name]
Syracuse, NY 13210

Statistical Methods

The analysis will be performed under the responsibility of Upstate Medical University in conjunction with the study partners.

This will be a descriptive study to assess immunogenicity of a licensed rabies vaccine using test dosage schedules and routes of administration. No formal statistical hypothesis tests will be conducted. Descriptive analyses for the primary endpoints will be based on per-protocol analysis data sets using the data from blood samples taken at baseline (0 days), 28 days, and 365 days after the initial dose and at 7 days after a booster at one year (372 days). Separate descriptive analyses will be conducted for each per-protocol data set and group.

Exploratory statistical analyses of final data may be conducted, if indicated by the descriptive results. Parametric, non-parametric and resampling (bootstrapping) methods for statistical inference may be used in exploratory analyses, based on data compliance with assumptions of methods. P -values ≤ 0.05 will be considered significant and p-values ≤ 0.10 will be considered a trend. Confidence intervals will be constructed at $\alpha=0.05$ and $\alpha=0.10$. When necessary, p-value corrections for multiple comparisons will be applied.

A descriptive summary of adverse events that were reported throughout the trial will be produced.

Descriptive and inferential analyses (if any) will be carried out using SAS Version 9.2 (or more recent versions), which is licensed and supplied by SAS Institute, Cary, NC, USA.

Per-Protocol Analysis Set

The Per-Protocol (PP) analysis set will include all subjects who had no protocol deviations at the time that the data was collected. Three PP analysis sets will be produced for the primary objective that will contain separate data from blood drawn on day 0, day 28 and day 372, respectively. Descriptive analysis of the secondary endpoint will require a fourth per protocol analysis set for blood drawn on day 365. Subjects will be excluded from the PPAS for the following reasons:

1. Subject did not meet all protocol-specified inclusion/exclusion criteria or definitive contraindications (only for the second and third vaccination)
2. Subject did not receive the correct number of injections
3. Administration of vaccine was not done as per protocol (site and route of administration)
4. Subject did not receive vaccine in the proper time window defined in the tables of the study procedures
5. Subject did not provide a post-dose serology sample in the proper time window defined in the tables of the study procedures

Subjects will remain in this population as long as they do not meet one of the above criteria, except for blood sampling timing and validity of the serology test result*. A PP set will be defined for each injection.

***Note:** For example, a subject whose time period is outside the defined visit window only between the first injection and the blood sample taken after the first injection will be excluded from PP1 but may be kept in PP2 or PP3.

Subjects will be analyzed by the vaccine group to which they were randomized, subject to the exclusion criteria above

Full Analysis Set

The full analysis set (FAS) is defined as the subjects who received at least one injection of Rabies vaccine and had at least one blood sample drawn and valid post-injection serology result (i.e. a result different from “NR” or missing).

Subjects will be analyzed by the treatment group to which they were randomized.

Populations Used in Analyses

The immunogenicity analysis will be performed on the PP. The kinetic analysis will be performed on the FAS.

Handling of Missing Data and Outliers

Immunogenicity

For the computation of GMTs, a titer reported as < LLOQ will be converted to a value of 0.5 LLOQ.

For calculating fold-rise and titer ratio (GMTR), < LLOQ will be converted to 0.5 LLOQ for a numerator and < LLOQ will be converted to LLOQ for a denominator

Any titer reported as > ULOQ (upper limit of quantization) will be converted to ULOQ.

Missing data will not be imputed.

Potential outliers will be identified using histograms and modified box plots or normal probability plots, when appropriate. Choice of subsequent tests for outliers (e.g. Grubbs, Tietjen-Moore and ESD) will depend on the number and nature of suspected outliers and may require data transformation. .
Bootstrapped estimates of standard errors may also be reported. Sensitivity analysis of effect of outliers on descriptive statistics will be conducted, and if necessary descriptive statistics that include and exclude outliers will be reported

Statistical Methods for Baseline Comparisons

Mean (SD) and median (IQR) age at baseline will be computed and descriptively compared across the six groups. Results will be presented in tabular format.

The number and percentage of males and females per group at baseline will be calculated and results will be presented in tabular format.

Baseline mean (SD) and median (IQR) of all other quantitative demographic variables of interest will be calculated for each group and the results will be presented in a table.

The number and percentage per group at baseline of all other qualitative demographic variables of interest will be calculated for each group and the results will be presented in tabular format.

Statistical Methods for Subject Disposition

For each group, the number and percentage of subjects who received a total of 0, 1, 2, 3 and 4 rabies vaccinations will be reported in tabular format.

Statistical Methods for Primary Immunogenicity Objectives

Immunogenicity against rabies will be assessed descriptively using the following parameters:

Timepoints: At baseline, 28 days and 372 days.

- Number and percentage of subjects with a titer ≥ 0.5 IU/ml against rabies virus by treatment group at days 0, 28 and 372.

A table that presents the total number of per-protocol subjects and the number and percent of each treatment group who have a titer ≥ 0.5 IU/ml against rabies virus at days 0, 28 and 372 will be produced.

Statistical Methods for Secondary Immunogenicity Objectives

Immunogenicity will be assessed descriptively using the following parameters:

Timepoints: Days 0, 28 and 365.

A table that presents, by treatment group, the total number of per protocol subjects and the number and percent of each group who have IgG titers ≥ 0.5 IU/ml against rabies virus at days 0, 28 and 365 will be produced.

Statistical Methods for Adverse Events and Serious Adverse Events

For each treatment group, a line listing by subject that describes adverse events and post-baseline day of occurrence of the AE will be produced.

The number and percent of subjects in each group who reported any AE between Days 0 and 372 will be summarized in tabular format.

A table showing the number and percentage of subjects in each group who reported adverse events by general type (category) of event will be produced.

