5.1 Justification of the Trial Design

This exploratory study is designed to be a broad evaluation of the immune response, in healthy adults, to vaccination with rabies vaccine across a variety of vaccination scenarios. The goal is to characterize the host response in four vaccination schedules.

Evaluation will be focused on antibody response to trial regimens in relation to using the accepted rabies vaccination schedule. The goal is to evaluate host response to the delivery of a licensed vaccine using an ID delivery and a 2 dose schedule compared to the recommended vaccination schedule of 3 doses by IM delivery, using descriptive statistical methods and exploratory data analysis.

The placebo (human serum albumin) groups will have proteomic analyses performed. This will show any differences in the proteomic responses that are due to the mechanical differences in the different routes of administration.

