6.7.2 Definitive Contraindications

Should a subject experience one of the conditions listed below, the Investigator will discontinue vaccination:

- Pregnancy, as indicated by a positive urine test on vaccination days.
- An anaphylactic or other significant allergic reaction to the previous dose of vaccine
- Known or suspected congenital or acquired immunodeficiency; or receipt of immunosuppressive therapy such as anti-cancer chemotherapy or radiation therapy within the preceding 6 months; or long-term systemic corticosteroid therapy (prednisone or equivalent for more than 2 consecutive weeks within the past 3 months)
- SAE related to the study vaccine following the trial vaccination
- Participation in another clinical trial investigating a vaccine, drug, medical device, or medical procedure
- Deprived of freedom by an administrative or court order, or in an emergency setting, or hospitalized involuntarily. Subjects will not be withdrawn due to contraindication but will be followed up for safety and possibly immunogenicity assessment.

Note: If a subject who has already received at least 1 dose of the study vaccine, experiences a contraindication to further vaccination during the trial, they will continue to be followed for immunogenicity assessments and will not be discontinued from the trial; however, no additional vaccinations will be administered.

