6.10.2 Follow-up and Reporting of Pregnancies

Pregnancy is an exclusion criterion for enrollment in this study, but a subject could potentially become pregnant during her participation. In case of pregnancy and if at least one dose of the study vaccines has been administered, the subject will not be discontinued from the trial and will

be followed for immunogenicity assessment. However, no additional vaccination will be administered.

All pregnancy cases should be reported if they occurred during the study. Study staff must then maintain contact with the subject to obtain information about the outcome—i.e., details about the delivery and the newborn, or about pregnancy termination.

Pregnancy itself is not considered an AE, but any complications during pregnancy are to be considered as AEs, and in some cases could be considered SAEs. Spontaneous abortions, fetal death, stillbirth, and congenital anomalies reported in the baby are always considered as SAEs, and the information should be provided using an SAE form.

7 Safety Emergency Coverage

Subjects in the trial will be given contact numbers for the PI and study team members in the event of an emergency related to the trial. A study investigator will be available at all times for study related emergencies. If emergency health care is needed, subjects should seek care through the 911 system or local emergency services. Study team contact numbers should be used to notify the study team of an emergency after emergent health care issues have been handled.

8 Modification of the Trial and Protocol

Any amendments to this trial plan and protocol must be discussed with WRAIR. If agreement is reached concerning the need for an amendment, the PI will be responsible for completing the amendment and creating a new version of the protocol will replace the earlier version. All substantial amendments e.g. that affect the conduct of the trial or the safety of subjects, require IRB approval, and must also be forwarded to regulatory authorities.

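### The two immunogenicity tables report only per-protocol n and % by group, with no interval, no difference from the 3-dose IM arm and no repeat on the full analysis set

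*SAP*

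**What the plan says.** **The tables.** The SAP section on the primary immunogenicity objectives specifies "A table that presents the total number of per-protocol subjects and the number and percent of each treatment group who have a titer" of at least 0.5 IU/ml at days 0, 28 and 372. The section on the secondary objectives specifies "A table that presents, by treatment group, the total number of per protocol subjects and the number and percent of each group" at or above the same IgG threshold at days 0, 28 and 365. Nothing else is listed for either. Protocol 20.1 leaves the choice of descriptive statistics to the SAP.

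**Intervals.** The SAP's Statistical Methods section does say that confidence intervals will be constructed, at alpha 0.05 and 0.10. That sentence stands in the paragraph that opens "Exploratory statistical analyses of final data may be conducted, if indicated by the descriptive results". It names no method and no parameter, and refers to neither table.

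**Comparison.** Protocol 5.1 gives the goal as evaluating ID delivery and a 2-dose schedule "compared to the recommended vaccination schedule of 3 doses by IM delivery, using descriptive statistical methods and exploratory data analysis". No between-group difference is specified in either document.

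**Populations.** Under Populations Used in Analyses the SAP states: "The immunogenicity analysis will be performed on the PP. The kinetic analysis will be performed on the FAS". Grounds for leaving the per-protocol (PP) set include "Subject did not receive the correct number of injections" and a dose outside its window. The FAS takes subjects with at least one rabies vaccine injection and a valid post-injection serology result, by randomized group. The SAP neither defines the kinetic analysis nor gives it an output.

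**Follow-up after dosing stops.** Protocol 6.7.2 says of subjects who meet a contraindication after at least one dose that "they will continue to be followed for immunogenicity assessments and will not be discontinued from the trial". Under Protocol 6.10.2 a subject who becomes pregnant after at least one dose stays in the trial, to "be followed for immunogenicity assessment. However, no additional vaccination will be administered".

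**The concern.** There are two gaps.

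The first is precision. The trial was set up to describe shorter and ID schedules against 3-dose IM, but its main tables would state neither that contrast nor its uncertainty. Two arms both at 100% on 12 subjects can easily be read as showing that the schedules match. The method and level of any interval are also left open until the results are known.

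The second is population. Subjects whose dosing stops for a contraindication or pregnancy stay in immunogenicity follow-up and still give blood, but having missed a scheduled dose they fall out of the PP set. No specified table reports whether they reached 0.5 IU/ml. The PP total set against 12 randomized shows how many were left out, but not their response.

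**Working it through.** **Inputs.** The Synopsis gives 12 subjects in each of Groups 1 to 4 and 6 in each of Groups 5 and 6. Protocol 22 gives a total of 60 allocated 2:2:2:2:1:1. This reproduces: 60 × 2/10 = 12, 60 × 1/10 = 6, and 4 × 12 + 2 × 6 = 60. The plan states no power, precision, expected response or exclusion rate, so the response and exclusion counts below are assumptions shown over a range.

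**One group.** The Wilson interval is [p + z²/2n ± z√(p(1−p)/n + z²/4n²)] / (1 + z²/n). When all n respond, the lower limit reduces to n/(n + z²). With z² = 3.8415 for 95%:

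- 12/12: 12/15.8415 = 75.8%, so 75.8% to 100%. The Clopper-Pearson interval is 73.5% to 100%.
- 11/12: 64.6% to 98.5%.
- 10/12: 55.2% to 95.3%.
- 10/10: 10/13.8415 = 72.2%, so 72.2% to 100%.

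**Difference from Group 1.** With Wilson limits (l, u), subscript X for the other group and 1 for Group 1, and d = pX − p1, Newcombe's limits are

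- lower: d − √[(pX − lX)² + (u1 − p1)²]
- upper: d + √[(uX − pX)² + (p1 − l1)²]

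For 12/12 against 12/12, d = 0. One squared term is zero in each limit, so the half-width is 100 − 75.8 = 24.2 points. At the 90% level, z² = 2.7055 and the half-width is 2.7055/14.7055 = 18.4 points. The other cases, with Group 1 at 12/12 throughout:

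| Group X | Difference (points) | Newcombe 95% |
|---|---|---|
| 12/12 | 0 | −24.2 to 24.2 |
| 11/12 | −8.3 | −35.4 to 16.9 |
| 10/12 | −16.7 | −44.8 to 10.4 |
| 9/12 | −25.0 | −53.2 to 4.1 |
| 10/10 | 0 | −27.8 to 24.2 |

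Miettinen-Nurminen limits lie within 1 point of every limit in this table (for 12/12 against 12/12 they are ±25.0), so the message does not depend on the method.

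The level matters more. For 9/12 against 12/12 the 95% interval includes zero, but the 90% interval is −48.7 to −1.6 and excludes it. The SAP names both levels without saying which applies.

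**PP against FAS.** Suppose k of 12 leave the PP set, the other 12 − k all respond, and those k have valid results on that day. The PP table then shows 100%, while the FAS lies between (12 − k)/12 and 12/12:

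- k = 1: PP 11/11 = 100%; FAS 11/12 = 91.7% to 100%.
- k = 2: PP 10/10 = 100% (Wilson 72.2% to 100%); FAS 10/12 = 83.3% (55.2% to 95.3%) to 100%. Up to 100 − 83.3 = 16.7 points would be unseen.

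**Time since last dose.** By the vaccination schedule, day 28 falls 28 − 21 = 7 days after the last dose in Groups 1 and 2, and 28 − 7 = 21 days after it in Groups 3 and 4. A day-28 difference of Group 3 or 4 from Group 1 needs that stated beside it.

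**The case against.** The plan is openly descriptive. Its objectives are to describe percentages, it attaches no hypothesis test, and Protocol 22 says it is not powered for equivalence or non-inferiority. Protocol 5.1 qualifies its comparison as descriptive and exploratory, which side-by-side percentages arguably satisfy. The tables print N and n, so a reader can work out any interval or difference. The sentence on intervals says they will be constructed, not that they may be. Three groups against Group 1 on three days makes nine unadjusted intervals, and one that excludes zero will tempt readers to treat it as a test.

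On population, the SAP has a disposition table counting vaccinations received, and the PP sets are specific to a time point, so a mistimed sample need not remove a subject from later sets. The 16.7-point figure needs two exclusions, both with valid results. A subject who missed the booster has no post-booster value at day 372, so PP is a reasonable lead set.

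Much of this stands, and it limits the seriousness of the point. The design is legitimate, nothing is concealed, and PP can remain the lead analysis. The risk of over-reading nine intervals is real and calls for an explicit label. But an interval or an estimated difference needs no test, margin or power claim. The sentence on intervals, read where it stands, belongs to optional work triggered by the results. Readers can recover intervals for the PP set, but not the titers of subjects outside it, and the disposition table counts doses rather than responses.

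**Conclusion.** The concern holds. Neither specified table carries an interval, no output estimates the comparison with 3-dose IM, and titers of incompletely dosed subjects who stay in follow-up appear in no specified table. If all 12 respond in both arms, differences of up to 24.2 points either way remain compatible with the data at the 95% level. With two PP exclusions out of 12 and full response in the rest, up to 16.7 points could go unseen. These sizes rest on assumed response and exclusion counts; fewer exclusions, or excluded subjects without a valid result, would shrink the second figure. The trial remains valid as a descriptive study. This is an inexpensive improvement that should be made. The undefined kinetic analysis is a drafting gap and adds no weight to the conclusion.

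**What to change.** In the SAP sections on the primary and secondary immunogenicity objectives:

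1. **Intervals and differences, Groups 1 to 4 only** (Groups 5 and 6 give blood for proteomics alone). Add a Wilson 95% interval to each percentage at days 28, 365 and 372. Show the differences of Groups 2, 3 and 4 from Group 1 with Newcombe 95% intervals. State that these are descriptive, not adjusted for multiplicity, and carry no hypothesis test. Footnote the 7 against 21 days since last dose at day 28.
2. **FAS repeat.** Produce both tables again on the FAS by randomized group, using subjects with a valid result on that day, in keeping with the no-imputation rule. In each cell show how many had missed a scheduled dose, including the booster at day 372.
3. **Kinetic analysis.** Define it, or remove the reference.

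The cost is SAP wording, a few columns and two repeat tables from data already collected. The stated precision will look less favourable, and the FAS tables mix fully and partly vaccinated subjects, which is why the missed-dose count is needed. Conduct, sample size and the descriptive character of the study do not change.
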